### 1.3. Study Population

This study will enroll patients with HER2 negative metastatic breast cancer whose treatment includes liposomal doxorubicin.. The enrolled patients will be treated with pegylated liposomal doxorubicin at 30mg/m^2 every 21 days

## 2. Trial Objectives

**Primary Objective:** To evaluate if low BRCA1 protein expression has a preferential effect on response when metastatic breast cancer patients are treated with DNA damaging chemotherapy agent.

**Secondary Objective:** To evaluate if low BRCA1 protein expression has a preferential effect on tumor progression when metastatic breast cancer patients are treated with DNA damaging chemotherapy agent.

## 3. Trial Design

### 3.1. Study Endpoints

**Primary Endpoint:** To correlate BRCA1 protein expression, as measured by IHC with overall response rate for metastatic breast cancer patients treated with pegylated liposomal doxorubicin. . The overall response rate is defined as the percentage of evaluable patients who achieve complete response (CR) or partial response (PR) as measured by RECIST 1.1 on CT or PET/CT as the best overall response

**Secondary Endpoint:** To correlate BRCA1 protein expression, as measured by IHC with median progression free survival for metastatic breast cancer patients treated with pegylated liposomal doxorubicin. The progression free survival is measured as the times from the start of pegylated liposomal doxorubicin to the time the patient is first recorded as having disease progression or dies.

3.2. **Study Design** This study is a prospective single arm Phase II trial to assess the association of BRCA1 protein expression with overall response rate in patients with HER2 negative metastatic breast cancer treated with pegylated liposomal doxorubicin. Patients who qualify for enrollment into the study will receive pegylated liposomal doxorubicin as a single agent intravenous at 30mg/m^2 every 21 days

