### Sample size determination

**Low BRCA1 protein expression:** Since it is expected only 30% of patients will have low BRCA1 protein expression, we will accrue 15 patients to this arm and estimate the response rate among these patients. With a sample size of 15 we will be able to estimate the response rate of 50% in patients with low BRCA1 protein expression with a 95% confidence interval width of  $\pm 25\%$ .

**Normal BRCA1 protein expression:** A Simon two-stage design will be used in which a 10% response rate is considered not promising, a 30% response rate is considered promising, and the probabilities of a type I error (falsely accepting a non-promising therapy) and type II error

(falsely rejecting a promising therapy) are set at 0.10 and 0.10, respectively. In this scenario, the maximum trial size would be 35 patients. In the first stage of this design, 12 patients with intact BRCA1 expression will be accrued. If at least two responses are observed among these 12 patients, then an additional 23 patients will be accrued to the second stage. If 0 or 1 response is observed among the initial 12 patients, then accrual to this cohort will be terminated and declared negative. At the end of the study if 6 or more patients in this cohort respond then pegylated liposomal doxorubicin will be considered worthy of further study in this cohort. This design yields at least 90% probability of a positive result if the true response rate is at least 30% and a 90% probability of a negative result if the true response rate is 10%.

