#### **Analytic plan for secondary objective:**

The progression free survival in patients with low BRCA1 protein expression and intact BRCA1 protein expression will be analyzed by Kaplan-Meier methodology. The results will be summarized by 25th, 50th (median), and 75th percentiles with associated 2-sided 95% confidence intervals,

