### **Methodology:**

**IHC staining for BRCA1:** Tumor samples will be reviewed to confirm adequate sample for staining. Tissues sections will be stained for BRCA1 by Genscript A00490 Rb polyclonal clone antibody using the Benchmark Ultra automated stainer (Ventana Medical Systems Inc, Tucson, Arizona). Low BRCA1 protein expression will be defined as  $\leq 5\%$  of cells staining with 1+ intensity of the tumor nucleus (i.e. nuclear long score  $\leq 5$ ). Intact BRCA1 protein expression will be defined as  $\geq 10\%$  of cells staining with 1+ intensity or  $\geq 5\%$  of cells staining with 2+ intensity of their nucleus (i.e. nuclear long score of  $\geq 10$ ). Nuclear long score of 6-9 i.e. 5-10% of cells staining with 1+ or  $< 5\%$  of cells stain with 2+ intensity, will be defined as indeterminate status.

**Quantitation of IHC:** Two Board Certified pathologists ([name], PhD and [name]) will evaluate each case using a semi quantitative histologic scoring method as previously described. Briefly, staining intensity for neoplastic cell's nucleus will be scored as: 0 negative, 1 weak, 2 moderate and 3 intense. In addition,

the percentage of positive neoplastic cells will be evaluated. The overall scores will be calculated by multiplying the intensity by the corresponding percentage of positive cells, resulting in a values ranging from 0 to 300. Low BRCA1 protein expression will be defined as nuclear long score of  $\leq 5$ , intact BRCA1 as nuclear long score of  $\geq 10$ , indeterminate BRCA1 expression as nuclear long score of 6-9.

**Chemotherapy agent:** Pegylated liposomal doxorubicin is frequently used in the salvage treatment of patients with metastatic breast cancer. It is a DNA damaging chemotherapy agent which has been reported to have a 25% overall response rate and 2.5 months median progression free survival in the salvage treatment of metastatic breast cancer. It has been shown to be safe in patients who have received prior anthracycline treatment.

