### 3.3. **Study Duration and Follow up**

All patients will be treated with pegylated liposomal doxorubicin until evidence of tumor progression. Patients will get a baseline CT or PET/CT scan prior to receiving pegylated liposomal doxorubicin. Repeat imaging at week 9 -12 ( $\pm$  7 days) will be performed to evaluate response. Subsequent imaging schedule will be left to the treating physician's discretion. All patients will be treated until documented disease progression, intolerable toxicity or withdrawal of consent.

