## 4. **Selection and Withdrawal of Patients**

### 4.1. **Inclusion Criteria:**

To be eligible for inclusion, each patient must have:

- 4.1.1 Metastatic breast cancer and have formalin-fixed, paraffin-embedded tumor available for testing BRCA1 protein expression
- 4.1.2 Adults over 18 years of age
- 4.1.3 Have resolution of all acute toxic effects of any prior chemotherapy or radiotherapy to NCI CTC grade  $\leq$  1 prior to study registration.
- 4.1.4 Be informed of the investigational nature of this study and provide written informed consent in accordance with institutional and federal guidelines prior to study specific screening procedures
- 4.1.5 Be willing and able to comply with the treatment plan, scheduled clinic visits, laboratory and oncological tests and other study procedures
- 4.1.6 Have a ECOG performance status of 0 – 2
- 4.1.7 Measurable disease by CT by RECIST 1.1 to evaluate response. Patients with bone only lesions are also eligible to enroll. Criteria to monitor for response will be based on non-target lesions per RECIST criteria
- 4.1.8 Adequate bone marrow function defined as platelets  $\geq$   $100 \times 10^9$  cells/L, neutrophils  $\geq$   $1.5 \times 10^9$  cells/L, white blood cells (WBC)  $\geq$   $3.0 \times 10^9$  cells/L and a hemoglobin  $\geq$  90 gm/L
- 4.1.9 Liver function tests (AST and/ or ALT) should be  $\leq$  2 x upper limit of normal (ULN, defined as per laboratory where blood testing is done), total bilirubin  $\leq$  1.5 x ULN (except for patients with liver metastases, ALT and/or ALT  $\leq$  5 times the upper limit of normal is accepted)
- 4.1.10 Patients who are already on pegylated liposomal doxorubicin will be eligible to participate in this study as long as they meet the other inclusion/exclusion criteria and can sign informed consent

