## 8. Study Statistics

8.1. **Statistical Methods:** This study is a prospective single arm Phase II trial to assess association of BRCA1 protein expression with overall response rate in patients with metastatic breast cancer on pegylated liposomal doxorubicin in patients with metastatic breast cancer. We plan to consent 50 to 60 patients with the goal of enrolling a total of 50 patients, with adequate primary tumor tissue for BRCA1 protein expression, into this study. It is estimated that 30% of patients will have low BRCA1 protein expression and therefore anticipate approximately a 35 to 15 patient split for normal BRCA1 to low BRCA1 expression status.

Recruitment and tissue analysis: Patients will be consented and after enrollment of the first 12 patients, a batch analysis of their tumors will be performed to analyze tumor BRCA1 protein expression. This will allow us to assign the patients to their respective cohorts (Normal BRCA1 protein expression and Low BRCA1 protein expression). This will be done until we have 12 patients in the normal BRCA1 protein arm. After that, an interim analysis will be performed for the normal BRCA1 arm and stopping rule will be applied as mentioned in the study design

8.2. **Analytic plan for primary objective:**

**Definition of primary endpoint:** Response rate is defined as the percentage of evaluable patients who achieve complete response (CR) or partial response (PR) as measured by RECIST on imaging as the best overall response.

**Low BRCA1 protein expression:** The number and percentage of patients falling into response category will be tabulated. The estimate of the response rate will be presented with 2-sided 95% exact binomial confidence intervals. We anticipate this data to be hypothesis generating and will form the basis for a future prospective clinical trial enrolling larger number patients to evaluate if low BRCA1 expression, as determined by IHC, is predictive of response to treatment with DNA damaging agents.

**Normal BRCA1 protein expression:** The estimate of the response rate will be presented with 2-sided 95% exact binomial confidence intervals. If 5 or fewer patients with response are observed among the 35 patients, then there will be no further investigation of the treatment. If 6 responses are observed out of 35 patients, there is 80% confidence that the true response rate >11.2%.

Interim analysis:

**Low BRCA1 protein expression:** No interim analysis will be conducted

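### The objectives ask whether low BRCA1 goes with better response and PFS, but sections 8.2 and 8.3 plan only side-by-side cohort summaries, with no low-versus-normal contrast or interval

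*Combined protocol and SAP*

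**What the plan says.** **The question.** Section 2 states the primary objective as "To evaluate if low BRCA1 protein expression has a preferential effect on response", and the secondary objective asks the same of tumor progression. Section 3.1 makes the primary endpoint "To correlate BRCA1 protein expression, as measured by IHC with overall response rate" and does likewise for median PFS. The title and section 3.2 speak of association.

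**The analysis.** For each cohort, section 8.2 plans a response rate with a two-sided exact 95% interval. The normal cohort also has a two-stage Simon rule (stop at 0 or 1 response in 12, otherwise continue to 35, positive at 6 or more). On the low cohort, section 8.2 adds "We anticipate this data to be hypothesis generating" and leaves the predictive question to a larger trial, for which these data are to be the basis. Section 8.3 plans a Kaplan-Meier median PFS per group. The synopsis says "The progression free survival in patients with low BRCA1 protein expression and intact BRCA1 protein expression will be analyzed by Kaplan-Meier methodology", summarised by quartiles with intervals.

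**The sizes.** Both are one-sample. For the low cohort the synopsis says "With a sample size of 15 we will be able to estimate the response rate of 50" percent, to within 25 points either way. For the normal cohort it uses 10% versus 30%, with both error rates at 0.10.

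**Classification.** The Methodology part of section 1.2 defines a third class, "indeterminate BRCA1 expression as nuclear long score of 6-9". Section 8 does not say how it is analysed.

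**The concern.** Preferential effect, correlation and association are all relations between expression groups. Neither cohort alone can show one, and nothing in section 8 or the synopsis names a difference, ratio, odds ratio, hazard ratio, log-rank test, regression or correlation with the IHC score.

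Readers will compare the groups anyway. For response they can subtract two rates, but the interval method and the handling of scores 6-9 would then be chosen after the data are known. Judging by eye whether two separate intervals overlap is not a valid substitute. For PFS, a hazard ratio cannot be recovered from group percentiles. The future trial that these data are meant to support would need both the size of the contrast and its uncertainty.

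**Working it through.** **1. The plan's own figures reproduce.**
- Simon rule (1/12, 5/35), exact binomial: type I error 0.098 at 10%, power 0.901 at 30%.
- Low cohort: 1.96 × √(0.5 × 0.5/15) = 25.3 points, matching the stated 25.

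Both are one-sample calculations, so neither sizes a contrast.

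**2. Half-width of the difference.** Inputs: 50% low rate, 15 low patients, and 35 or 12 normal patients (synopsis and section 8.2). The normal rate is taken as 10% or 30% (Simon rates) or 25% (the background rate for the drug in section 1.2; using it for the normal cohort is an assumption). Formula: 1.96 × √(0.25/15 + p(1−p)/n).

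| True normal rate p | n = 35 | n = 12 |
|---|---|---|
| 10% | 27.2 | 30.5 |
| 25% | 29.1 | 35.2 |
| 30% | 29.5 | 36.2 |

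**3. Example intervals (Newcombe, built from Wilson limits).** For 8/15 versus 9/35 the Wilson limits are 0.301 to 0.752 and 0.142 to 0.421. The difference is 0.533 − 0.257 = 0.276.
- Lower limit: 0.276 − √(0.232² + 0.164²) = −0.008.
- Upper limit: 0.276 + √(0.219² + 0.115²) = 0.523.

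| Normal responders of 35 | Low 8/15: points (95% CI) | Low 7/15: points (95% CI) |
|---|---|---|
| 4 | 41.9 (14.5 to 64.8) | 35.2 (9.0 to 59.5) |
| 5 | 39.0 (11.4 to 62.3) | 32.4 (5.8 to 56.9) |
| 9 | 27.6 (−0.8 to 52.3) | 21.0 (−6.3 to 46.9) |
| 11 | 21.9 (−6.6 to 47.3) | 15.2 (−12.2 to 41.8) |

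**4. Effect of the Simon rule.** Closure probability is P(X ≤ 1) with X binomial(12, p). The mean observed rate given closure is P(X = 1)/(12 × P(X ≤ 1)). At 10%: 0.282 + 0.377 = 0.659, and 0.377/(12 × 0.659) = 4.8%, about 5 points too low. The last two rows enumerate all outcomes under the stopping rule with a true low rate of 50%.

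| True normal rate | 10% | 25% | 30% |
|---|---|---|---|
| Closes at 12 | 66% | 16% | 8.5% |
| Bias of normal rate given closure (points) | −5 | −18 | −23 |
| Bias over all trials (points) | −2.3 | −1.9 | −1.3 |
| Interval wholly above zero | 80% | 43% | 29% |
| Newcombe coverage: all trials / given closure | 96.9% / 97.9% | 94.0% / 89.1% | 93.6% / 82.4% |

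**5. PFS hazard ratio.** The documents give no event count, so 25 to 50 events is an assumption. The 95% limits are the estimate divided and multiplied by exp(1.96/√(events × 0.3 × 0.7)): 1.83 for 50 events, 1.97 for 40, 2.18 for 30 and 2.35 for 25. If the normal cohort closes early, at most 15 + 12 = 27 patients contribute. Even if all 27 have events, the factor is exp(1.96/√(27 × 15/27 × 12/27)) = 2.14, against 1.83 if all 50 do.

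**6. Passages that bear on PFS and do not agree.**
- Section 3.3 says "Subsequent imaging schedule will be left to the treating" physician, as does 6.2.2. The table in 5.3 requires repeat imaging at least every 9 weeks.
- Section 4.1.10 says "Patients who are already on pegylated liposomal doxorubicin will be eligible to participate in this study". Sections 4.4 and 5.2 require registration before treatment starts.

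**The case against.** The strongest reply is that the study is openly exploratory: the low-cohort data are called hypothesis generating and the predictive question is deferred. That stands, and it disposes of one reading, that a confirmatory test is missing. It excuses low power, but not leaving out the quantity that the objective names.

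A reader might also infer that the plan never reports its primary endpoint. The documents do not support that. Response is reported for each BRCA1 group with an exact interval, which is a descriptive association; only the contrast and its interval are absent.

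A reader might take the anticipated 35 and 15, which sum to 50, to leave no place for scores 6-9. Section 8.1 calls the split approximate and plans to consent 50 to 60, so there may be room. What is missing is a rule for analysing those scores.

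A fixed 15 versus 35 comparison would put the chance of an interval above zero at 88%, 41% and 27% for normal rates of 10%, 25% and 30%. Those figures ignore the stopping rule; the 80%, 43% and 29% above apply to this trial.

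Finally, Newcombe and Cox are choices. Section 3.1 names median PFS, and "To correlate BRCA1 protein expression, as measured by IHC with overall response rate" could also be met with the 0 to 300 score. That is fair: the point is that some contrast be fixed in advance. The objection that the contrast is too imprecise carries less weight, because the plan already accepts 25 points either way for the low cohort alone.

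**Conclusion.** The concern holds as an omission of estimation and should be fixed. The objectives and endpoints are comparative, and the planned analysis stops at side-by-side summaries.

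The precision figures rest on a 50% low rate, a 10% to 30% normal rate and full cohorts of 15 and either 35 or 12. Both outcomes of the Simon rule matter, because at a true normal rate of 10% closure at 12 is the likelier one. After closure the observed normal rate is biased low. The contrast is then also partly non-concurrent, because section 8.2 goes on enrolling only low-expression patients.

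Hazard ratio precision is much less certain. A factor of about 1.8 to 2.4 each way reflects assumed event counts and should not be read as a figure the documents support. With one treatment and no control, even a reported contrast shows association only and cannot separate a predictive from a prognostic effect.

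**What to change.** - **Section 8.2:** pre-specify the low-minus-normal difference in response rate with a 95% interval (for example Newcombe) as the hypothesis-generating estimate for the primary objective. Leave scores 6-9 out of this two-group contrast and report them separately.
- **Expected precision:** state the half-width for both outcomes of the Simon rule, about 27 to 30 points for 15 versus 35 and about 30 to 36 points for 15 versus 12, with the assumed rates and closure probabilities.
- **Early closure:** state that the normal rate is then biased low and the contrast partly non-concurrent, and report it with that caveat.
- **Section 8.3:** add a Cox hazard ratio with a 95% interval, labelled exploratory, and say that its precision depends on the number of events.
- **Reconcile** the passages on later imaging (3.3 and 6.2.2 against 5.3) and on patients already on the drug (4.1.10 against 4.4 and 5.2).
- **Interpretation:** state that a single-treatment trial shows association only.

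The per-cohort estimates, the Simon rule and accrual stay as they are. If the sponsor does not want a contrast, the alternative is to reword the objectives and endpoints as per-cohort estimation.

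The cost is some SAP wording and a few lines of analysis, with no new patients. The downside is that the interval will be wide and may include zero even if the effect is real.

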### 3.3. **Study Duration and Follow up**

All patients will be treated with pegylated liposomal doxorubicin until evidence of tumor progression. Patients will get a baseline CT or PET/CT scan prior to receiving pegylated liposomal doxorubicin. Repeat imaging at week 9 -12 ( $\pm$  7 days) will be performed to evaluate response. Subsequent imaging schedule will be left to the treating physician's discretion. All patients will be treated until documented disease progression, intolerable toxicity or withdrawal of consent.

## 4. **Selection and Withdrawal of Patients**

### 4.1. **Inclusion Criteria:**

To be eligible for inclusion, each patient must have:

- 4.1.1 Metastatic breast cancer and have formalin-fixed, paraffin-embedded tumor available for testing BRCA1 protein expression
- 4.1.2 Adults over 18 years of age
- 4.1.3 Have resolution of all acute toxic effects of any prior chemotherapy or radiotherapy to NCI CTC grade  $\leq$  1 prior to study registration.
- 4.1.4 Be informed of the investigational nature of this study and provide written informed consent in accordance with institutional and federal guidelines prior to study specific screening procedures
- 4.1.5 Be willing and able to comply with the treatment plan, scheduled clinic visits, laboratory and oncological tests and other study procedures
- 4.1.6 Have a ECOG performance status of 0 – 2
- 4.1.7 Measurable disease by CT by RECIST 1.1 to evaluate response. Patients with bone only lesions are also eligible to enroll. Criteria to monitor for response will be based on non-target lesions per RECIST criteria
- 4.1.8 Adequate bone marrow function defined as platelets  $\geq$   $100 \times 10^9$  cells/L, neutrophils  $\geq$   $1.5 \times 10^9$  cells/L, white blood cells (WBC)  $\geq$   $3.0 \times 10^9$  cells/L and a hemoglobin  $\geq$  90 gm/L
- 4.1.9 Liver function tests (AST and/ or ALT) should be  $\leq$  2 x upper limit of normal (ULN, defined as per laboratory where blood testing is done), total bilirubin  $\leq$  1.5 x ULN (except for patients with liver metastases, ALT and/or ALT  $\leq$  5 times the upper limit of normal is accepted)
- 4.1.10 Patients who are already on pegylated liposomal doxorubicin will be eligible to participate in this study as long as they meet the other inclusion/exclusion criteria and can sign informed consent

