#### **Interim Analysis**

**Low BRCA1 protein expression:** No interim analysis will be conducted

**Normal BRCA1 protein expression:** An interim analysis for futility will be conducted in this group. The response rate will be used as the endpoint for the interim analysis for this group. The interim analysis will be performed when the first 12 treated patients are accrued. Based on Simon's 2-stage design, if less than 2 responders are observed out of these initial 12 evaluable patients in normal BRCA1 protein expression, patient enrollment will be discontinued into this arm. Otherwise patient enrollment will continue until a total of 35 patients evaluable for response are enrolled. If only 1 response is observed out of 12 patients, there is 80% confidence that the true response rate <22.1%.

**Feasibility Issues:** Patients with metastatic breast cancer (exclude Her-2/neu patients) whose primary tumor tissue is available for assessing defective DNA repair will be identified by the medical oncologists at the University of Arizona Cancer Center and the University of New Mexico to be included and treated with pegylated liposomal doxorubicin in the salvage setting. During the past year we have treated more than 25 patients with metastatic breast cancer with liposomal doxorubicin. We anticipate to complete accrual of 50 patients in 2 years. If we do not

accrue as expected after year 1, we plan to expand enrollment to other institutions we are currently collaborating (University of Washington and University of New Mexico).

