##### 6.2.1. **Baseline assessment**:

To assess response, it is necessary to estimate the tumor burden at baseline before the start of treatment. Subsequent measurements will be compared to this. Measurable disease is defined by the presence of at least one lesion that can be accurately measured in at least one dimension (longest diameter recorded) as  $\geq 2.0$  cm with conventional techniques or as  $\geq 1.0$  cm by spiral CT scan. All lesions that do not fit these criteria are considered to be non-measurable disease. All measurable lesions up to a maximum of five lesions per organ and ten lesions in total should be identified as target lesions and be recorded and measured at baseline. Target lesions should be selected on the basis of their size (those with longest diameter) and their suitability for accurate repeated measurements. A sum of the longest diameter for all target lesions will be calculated and reported as the baseline sum. This will be used as the reference for characterizing the objective tumor response

6.2.2. **Tumor assessments** will be made during screening and then at 9 (± 7 days) weeks to evaluate response rate. There after the use of further imaging for tumor assessment will be left to the treating physicians discretion

6.2.3. **Evaluation of target lesions**

Tumor response will be evaluated as follows (see appendix 2, Recist 1.1)

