**Evaluation overall**  
The best response is from the start treatment and imaging done weeks (± 7

6.2.5 **Response rate:** The clinical response rate is the percentage of evaluable patients who achieve complete response (CR) or partial response (PR) as the best overall response.

6.2.6 **Progression-free survival:** will be measured as the time from the start of pegylated liposomal doxorubicin to the time the patient is first recorded as having disease progression or dies. If a patient does not progress or die while being followed via tumor assessment, progression-free survival will be censored at the time of last disease assessment.

7. **Study Drug Information**

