## Appendix 2. Response Evaluation Criteria in Solid Tumors (RECIST 1.1)

### Eligibility

- Only patients with measurable disease at baseline should be included in protocols where objective tumor response is the primary endpoint.

**Measurable disease** - the presence of at least one measurable lesion. If the measurable disease is restricted to a solitary lesion, its neoplastic nature should be confirmed by cytology/histology.

**Measurable lesions** - lesions that can be accurately measured in at least one dimension with longest diameter  $\geq 20$  mm using conventional techniques or  $\geq 10$  mm with spiral CT scan.

**Non-measurable lesions** - all other lesions, including small lesions (longest diameter  $< 20$  mm with conventional techniques or  $< 10$  mm), i.e., bone lesions, leptomeningeal disease, ascites, pleural/pericardial effusion, inflammatory breast disease, lymphangitis cutis/pulmonis, cystic lesions, and also abdominal masses that are not confirmed and followed by imaging techniques; and

- All measurements should be taken and recorded in metric notation, using a ruler or calipers. All baseline evaluations should be performed as closely as possible to the beginning of treatment and never more than 4 weeks before the beginning of the treatment.
- The same method of assessment and the same technique should be used to characterize each identified and reported lesion at baseline and during follow-up.
- Clinical lesions will only be considered measurable when they are superficial (e.g., skin nodules and palpable lymph nodes). For the case of skin lesions, documentation by color photography, including a ruler to estimate the size of the lesion, is recommended.

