### Evaluation of non-target lesions

* Complete Response (CR):	Disappearance of all non-target lesions and normalization of tumor marker level
* Non-CR/Non-PD	Persistence of one or more non-target lesion(s) or/and maintenance of tumor marker level above the normal limits
* Progressive Disease (PD):	Appearance of one or more new lesions and/or unequivocal progression of existing non-target lesions (1)

(1) Although a clear progression of “non target” lesions only is exceptional, in such circumstances, the opinion of the treating physician should prevail and the progression status should be confirmed later on by the review panel (or study chair).

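### The denominator of the primary response rate, and of the 2/12 and 6/35 rules, rests on an undefined term that conflicts with Appendix 2, and bone-only patients cannot be fully coded

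*Combined protocol and SAP*

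**What the plan says.** **Denominator.** Section 6.2.5 states: "The clinical response rate is the percentage of evaluable patients who achieve complete response (CR) or partial response (PR". Section 8.2 repeats it: "Response rate is defined as the percentage of evaluable patients who achieve complete response (CR) or partial response (PR". The synopsis (Primary Endpoint and Statistical Methods) and section 3.1 use the same term. No section defines *evaluable*.

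**Interim and final counts.** In the synopsis (Interim Analysis) and section 8.2, the interim look comes once 12 treated normal-BRCA1 patients have been accrued. The stopping rule is then worded for evaluable patients: "if less than 2 responders are observed out of these initial 12 evaluable patients in normal BRCA1 protein expression". Accrual otherwise runs to 35 patients described as evaluable for response.

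**Unassessable patients.** The best-response table in section 6.2.4 has an NE outcome but does not say whether NE patients stay in the denominator. Section 6.2.3 sends the reader to the appendix: "Tumor response will be evaluated as follows (see appendix 2, Recist 1.1". There, Reporting of results puts every eligible patient in the main analysis, counts response categories 4-9 (which include not assessable) as failures, and leaves the precise definitions to the protocol.

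**Bone-only patients.** Section 4.1.7 says "Patients with bone only lesions are also eligible to enroll" and "Criteria to monitor for response will be based on non-target lesions per RECIST criteria". Appendix 2, Eligibility, says "Only patients with measurable disease at baseline should be included in protocols where objective tumor response is the primary endpoint" and lists bone lesions as non-measurable.

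**The concern.** Two questions that decide the primary result are left open.

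1. **Does an unassessable patient count as a failure, or is the patient dropped and replaced?** Appendix 2 says failure. The phrase about 35 patients evaluable for response can be read as replacement. Such patients are foreseeable: section 4.3 lists loss to follow-up, refusal, toxicity and a new treatment as reasons for withdrawal, and a patient who leaves before the week 9-12 scan has no on-treatment imaging. Dropping patients who leave early tends to raise the response rate if they are mostly non-responders.

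2. **How is a bone-only patient scored and counted?** Eligibility lets them in, Appendix 2 would keep them out, and the response tables cannot fully code them.

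At stake are the 2/12 and 6/35 decisions in the normal-BRCA1 cohort, the meaning of the stated 10% and 30% rates, and the denominator of the low-BRCA1 estimate. If the denominator is settled only after the first 12 patients' responses are known, the choice can be influenced by them.

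**Working it through.** **Step 1. Reproduce the design.** Inputs (synopsis, Sample size determination): stop if at most 1 of 12 respond; success if at least 6 of 35 respond; rates 10% and 30%.

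P(stop at 12) = (1-p)^12 + 12p(1-p)^11
- p = 0.10: 0.282 + 0.377 = 0.659
- p = 0.30: 0.014 + 0.071 = 0.085

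P(positive) = sum over x = 2 to 12 of P(X1 = x) · P(X2 ≥ 6 - x), with X1 ~ Bin(12, p) and X2 ~ Bin(23, p)
- p = 0.10: 0.098
- p = 0.30: 0.901

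Both agree with the plan's 0.10 and 90%. An exhaustive search also returns this as the Simon optimal design.

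**Step 2. Code a bone-only patient from the text.** All lesions are non-target. The Appendix 2 non-target categories are CR, Non-CR/Non-PD and PD. Anything short of complete disappearance is "Persistence of one or more non-target lesion(s", so PR is not available. In the tables of section 6.2.4 and Appendix 2, every CR, PR and SD row requires a target-lesion result. Only the progression and new-lesion rows clearly apply.

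**Step 3. Interim example (hypothetical data).** 12 treated, 1 responder, 2 unassessable.
- Appendix 2 rule: 1/12, below 2, so accrual stops.
- Evaluable with replacement: 1/10, so no decision yet. Two more patients enter and the bound is met if at least one responds: 1 - (1-p)^2 = 1 - 0.9^2 = 0.19, or 1 - 0.7^2 = 0.51. Here p is the rate among the replacements.

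With 2 or more responders among the 12, both readings continue. They can end differently only with 1 responder and at least 1 unassessable, or 0 responders and at least 2.

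**Step 4. Illustrations at assumed shares of 10% and 20%.** The documents give no shares.

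| Assumption | Formula | At 10% | At 20% |
|---|---|---|---|
| (a) 10%/30% describe measurable disease; share b is bone-only, no CR, and counted | rate p(1-b): 0.27, 0.24 against 30%; 0.09, 0.08 against 10% | power 0.846, type I 0.066 | power 0.764, type I 0.042 |
| (b) 10% describes all eligible; share f is dropped and replaced, none would respond | rate 0.10/(1-f): 0.111, 0.125 | type I 0.141 | type I 0.204 |
| (b) as above, dropped patients respond at half the overall rate | 0.10(1-f/2)/(1-f): 0.106, 0.1125 | type I 0.118 | type I 0.146 |
| (b) as above, dropped patients respond at the same rate | 0.10 | type I 0.098 | type I 0.098 |
| (c) Appendix 2 stops but replacement ends by passing 2/12; share f is unassessable, all non-responders | P(Bin(12, p) ≤ 1) - P(Bin(12, p/(1-f)) ≤ 1) | p = 0.10: 0.659 - 0.608 = 0.051; p = 0.30: 0.085 - 0.054 = 0.031 | p = 0.10: 0.659 - 0.547 = 0.112; p = 0.30: 0.085 - 0.029 = 0.056 |

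In (c), p is the rate among all eligible patients. In Step 3 it is the rate among replacements. On the basis of (c), the Step 3 probabilities become 0.21-0.23 and 0.56-0.61.

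**Step 5. Low-BRCA1 cohort (hypothetical data).** With 6 responders and 2 of 15 unassessable, the estimate is 6/15 = 40% (exact 95% CI 16-68%) or 6/13 = 46% (19-75%).

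**The case against.** The best defence is that Appendix 2 already supplies the rule. Section 6.2.3 refers to it, it counts unassessable patients as failures, and no section expressly provides for replacement. The interim text also refers back to the treated patients when it says evaluable, which suggests one group under two names. This is a fair reading, and the fix below largely restates it. It does not settle the matter: the endpoint definition and the target of 35 still say evaluable, the table's NE outcome has no stated place in the denominator, and Appendix 2 hands the detail back to the protocol.

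A reader might infer four stronger things that the documents do not support.

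- *The same interim data yield opposite decisions.* They do not. Under replacement, 1/10 means keep accruing. The eventual decision uses additional patients.
- *The error rates are wrong.* They are exact for whichever analysis set 10% and 30% describe.
- *The population for 10% and 30% is not named at all.* The normal-BRCA1 cohort is named. Only the analysis set within it is missing.
- *Admitting bone-only patients is itself the fault.* Entry looks deliberate, and section 4.1.7 says they are followed on non-target lesions. The fault is that their scoring and counting are unstated and that Appendix 2 says otherwise.

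It is also fair that every magnitude in Step 4 depends on assumed shares, and that one branch of (b) shows no change.

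**Conclusion.** The point holds and should be fixed. The body and Appendix 2 conflict on who belongs in the primary denominator, and bone-only patients who do not progress cannot be coded from either response table. This goes beyond missing detail, because one permissible reading lets unassessable patients be dropped and replaced. That can bias the response rate upward and can change whether the normal-BRCA1 cohort passes 2/12.

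The firm results are the reproduced design (0.098 and 0.901) and the example (stop at 1/12, against continued accrual with a 0.19 or 0.51 chance of passing). At assumed shares of 10-20%, the two readings end the interim stage differently with probability 0.05-0.11 at a true 10% and 0.03-0.06 at a true 30%. Power could be 0.85-0.76 under (a), or type I error 0.10-0.20 under (b). These effects oppose each other, so the net direction is unknown. The error rates concern the normal-BRCA1 cohort only; the low-BRCA1 cohort has no stopping rule and shares only the denominator ambiguity.

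**What to change.** 1. Replace *evaluable* in the synopsis (Primary Endpoint, Statistical Methods, Interim Analysis) and in sections 3.1, 6.2.5 and 8.2 (endpoint definition and interim text) with: all eligible treated patients in the cohort; patients with NE or Appendix 2 categories 4-9 count as non-responders and are not replaced. Apply this to the 2/12 rule, the 6/35 rule and the low-BRCA1 estimate. The stopping-rule text in section 9 does not use the word, but its counts of 12, 23 and 6 should be tied to the same set.
2. Reconcile section 4.1.7 with Appendix 2 by stating that bone-only entry is an exception to the measurable-disease rule.
3. Add rows for non-target-only disease to the tables in section 6.2.4 and Appendix 2: CR; Non-CR/Non-PD, counted as non-response; PD.
4. Report the response rate in measurable-disease patients alongside the primary rate.
5. State which analysis set 10% and 30% describe. If measurable disease was meant, restate the power for the mixed population (about 0.85-0.76 at an assumed 10-20% bone-only share with no CR). If the mixed population was meant, 30% overall corresponds to 0.30/0.90 = 33% or 0.30/0.80 = 37.5% in measurable disease on the same assumption.

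**Cost.** No extra patients. The reported response rate may be slightly lower, and the stated power may be less favourable. The wording should be settled before the 12-patient look.
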